### 6.2.3. Study Treatment

[figure not shown]
## 6.2.3.1. Treatment with RZL-012 Investigational Therapy

RZL-012 is an investigational product supplied as a single dose single treatment injection in multiple sites (8-48) of injections. Before injection, subjects will be advised to keep their regular diet and physical activity.

The injection dosing regimen and technique is crucial for the therapy safety and efficacy. Syringes will be filled by the pharmacist with 0.1 mL RZL-012 or vehicle and the number of syringes will be compatible with the number of injections. All injections will be administered diagonally in 45 °, using a 1 mL Luer-lock syringe and a 30 G x 1/2" needle.

[figure not shown]
The injection will be administrated randomly into the left or right abdominal subcutaneous fat according to the randomization scheme (the hole of the needle pointing into the fat layer). A grid line will be drawn with a makeup pencil in a horizontal plane 5 cm lateral to the umbilicus lateral wall so that it will cut the injected points symmetrically (Figure 3).

Figure 3: RZL-012 Injection Sites

For the 1st, 2nd and 3rd cohorts one to four (depends on the number of injection sites) tick marks 2 cm apart will be drawn on the grid line. For the 4th cohort nine tick marks 1 cm apart will be drawn on the grid line. Thus, the distance between injected points will be 2 cm for the first 3 cohorts and 1 cm for the 4th cohort (Figure 4). The injection sites will be drawn with a makeup pencil. The needle will be inserted into the skin just above the pencil mark in a vertical manner towards earth. The hole of the needle should be pointing into the fat layer. An attempt to pull the plunger should be made before injecting to ensure that no blood is coming out. If so, the plunger should be pushed down to inject the medicine. The formulation is viscose; therefore, resistance is expected while injecting.

Figure 4: Design of the 24 Injection Sites

This study will be performed in a dose escalation manner:

#### **6.2.3.2.** Treatment with Placebo

Two subjects randomly assigned to the study in every cohort group will be injected placebo, which will be a vehicle control (tween-80, propylene glycol, benzyl alcohol and water) in the same manner as mentioned above (Section 6.2.3.1).

#### 6.2.4. Baseline Visit

Baseline visit is defined in the study as Day 0. Baseline visit will be performed to complete screening evaluation, and to review all procedures necessary to confirm subject eligibility. Subjects will stay overnight in the study center till 30h + 3h following drug injection.

Screening information may be considered for baseline data if acquired within the adequate timeframe as described in Table 2.

**Table 2: Subject Information and Timeframes** 

Information	Timeframe	Follow-up Timeframe
Informed Consent Form	Signed prior to any study dedicated procedure	
Medical History and Concomitant Medications	At screening visit and at clinic admission visit (Day -1)	
Physical examination	At screening Day1 visit and at Day 28	
Vital Signs	At screening Day 1 visit and at Days 0 (pre and following injection), 1, 7, 14, 21, 28	
Pulse rate	At Day 0 (pre and following injection) and at day 1	
ECG	At screening Day 1 visit, at Day 0 (following injection) and at Days 1, 14, 28	
Anthropometric Measurements: weight, height (screening only), BMI, waist circumference, hip circumference	At screening Day 1 visit, screening Day 2, clinic admission visit (Day-1) and at Day 28	Every 28 days. On Days 56, 84, 112, 140, 168
Weight – measured at home by the subjects at morning (8-12h fast) and at bedtime	At Days 7, 14 and 21	Every week when not visiting the site
Draize Score at the Injected Site	At screening Day 1 and at Days 0 (pre- and following injection), 1, 7, 14, 21, 28	Every 28 days.
Serology assays (HBV, HCV and HIV)	At screening day1 visit	
Urine drug screen	At screening Day 1 visit and at clinic admission visit (Day -1)	
Serum chemistry	At screening Day 1, at clinic admission visit (Day -1) and at Day 1, 3, 7, 14 and 28	
Hematology	At screening Day 1, at clinic admission visit (Day -1) and at Day 1, 3, 7, 14 and 28	
Fasting Glucose	At screening Day 1	
Fasting Glucose, Insulin, Leptin, Lipid Profile and FFA	At clinic admission visit (Day -1) and at Day 28	Every 28 days. On Days 56, 84, 112, 140, 168
Urinalysis	At screening Day 1 visit and at Days 14, 28	

Information	Timeframe	Follow-up Timeframe
Cytokines and inflammatory markers— in subjects from the 2 nd , 3 rd and 4 th cohorts	At clinic admission visit (Day -1) visit and at Days 7, 14, 21 and 28	
Histamine	At clinic admission visit (Day -1), and at Day 1, 3 and 14	
Pharmacokinetics in subjects from all cohorts	At Day 0-1	
Photography of the Injected Sites	At screening Day 1 visit and at Days 1, 7, 14, 21, 28	Every 28 days. On Days 56, 84, 112, 140, 168
Thermal Imaging	At screening Day 1 visit,at clinic admission visit (Day - 1)and at Days 1, 7, 14, 21, 28	On Day 56
Thermal Imaging - in subjects from the 3 rd and 4 th cohorts (or in cohort 2 if 2 subjects experience intolerable side effects within the 3 rd cohort)		Every 28 days. On Days 56, 84, 112, 140, 168
MRI	At screening Day 2 and at Day 28	
MRI - in subjects from the 2 nd cohort		On Day 56
MRI - in subjects from the 3 rd and 4 th cohorts (or in cohort 2 if 2 subjects experience intolerable side effects within the 3 rd cohort)		Every 28 days. On Days 56, 84, 112, 140, 168
Biopsy – in subjects from the 3 rd cohort or in cohort 2 if 2 subjects experience intolerable side effects within the 3 rd cohort		On Day 56
AE Assessment	At Days 1, 3, 7, 14, 21, 28	Every 28 days
Cohorts 1 and 2: AE Assessment by phone	Days 84 and 112	

## 6.2.5. Subject Site Visits

Subject site visits will be performed  $\pm$  1 days from scheduled date for study visits Day 0-28 and  $2\pm$  1 days from schedule date for follow-up visits (Day 56-168). All data relevant for the visit needs to be obtained within 3 days (e.g., blood tests) of visit.

Subject sites visits will include procedures as described in Appendix I - Trial Schedule of Events.

For site visit that results in study discontinuation, see termination visit in Section 6.2.6.

#### 6.2.6. Termination Visit

Once study is discontinued, all reasonable measures should be taken to perform a termination visit. Termination visit should include all procedures necessary to complete subjects' records: AE reporting, any clinical laboratory test needed to evaluate unresolved AEs, evaluation of response, recovery of all clinical supplies and compliance diaries, and updating of subject contact information.

#### 6.2.7. Unscheduled Visit

Unscheduled visits will be performed upon investigator's discretion, upon Sponsor request to redo tests with unusual results or complete missing results and may occur upon subject's decision with no notification in advance. Unscheduled visits will include any study procedure deemed necessary, as described in Section 6.1.

#### 7. SAFETY CONSIDERATIONS AND GUIDANCE FOR INVESTIGATORS

Adherence to protocol monitoring procedures along with the following safety guidance will aid and promote subject safety.

### 7.1. STUDY RESTRICTIONS REGARDING CONCOMITANT MEDICATIONS

Subjects may not receive the following medications while on study:

- Chronic treatment with systemic steroids or immunosuppressive drugs.
- Chronic treatment with Non Steroid Anti-Inflammatory Drugs (NSAIDs).
- Any investigational product other than RZL-012.

Before dosing, analgesic gels such as Lidocaine or Pramoxine should be used to numb the injected site. An ice pack may be applied on the site of injection following dosing to help reduce pain. At day 3 following blood sampling for histamine, the anti-histamine Benadryl Gel (Dimethindene Maleate 0.1 %) for topical use only should be initiated according to drug instructions for use to avoid itching in the injected area. Benadryl Gel should be applied for 7 days.

Use of supplements or complementary medicines/botanicals and high energy supplements or drinks is prohibited, except for conventional multivitamin supplements.

#### 7.2. SAFETY MEASUREMENTS

Simple measures may help avoid specific AEs associated with the use of the RZL-012 investigational product. Thus, study subjects must be informed of possible AEs that occurred in animal studies (rats and pigs):

- Any injection site reaction may occur. Pain, swelling, itching, edema, erythema, hematoma etc.
- Slight transient injection site bleeding following injection may occur.
- Itching in the injected area may occur, and study subjects should be advised to use an antihistamine gel for topical use according to drug recommendations, wear wide cotton shirts, prevent touch with irritable clothing, avoid scratching and avoid exposure to direct sun. Itching is expected till 7 days following drug injection.
- Local erythema in the injected area.
- Local heat in the injection area.
- Study restrictions regarding concomitant medications are listed in Section 7.1.
- The local subcutaneous fat reduction may appear as a slight dip in the skin surface. This decline may be temporary and transient.
- Transient increase (72%) in the WBC count by 24 hours following injection, which returned to basal level after 14 days. Probably associated with the inflammatory response at the site of injection and involve neutrophils, monocytes and eosinophils.
- Increased level of BUN and of creatinine and minimal single cell necrosis was observed in tubular epithelium at cortico medullary junction of kidney in rats receiving a dose higher 25 times the highest dose in this study. All abnormalities were found to be reversible by Day 14.
- Increased AST level which is most typical of myofiber injury associated with study related procedures. This elevation was found to be reversible by Day 14.
- Transient increase of serum CRP levels (in rats) which returned to the basic level by 14 days.
- Marked irritancy in the injected subcutaneous tissue resulting in coagulation necrosis of relatively large areas in the subcutaneous tissue planes acutely. Necrosis persisted for up to 14 days and was accompanied by early evidence of healing in the form of chronic inflammation and fibrosis.
- Local inflammation (minimal to moderate) with muscle degeneration, epidermal/dermal necrosis (minimal to severe) and parakeratosis (minimal). Inflammation observed at injection site was also extended to adjacent subcutaneous adipose tissue. By 56 days the inflammation was minimal, muscle degeneration was not evident and inflammation to adjacent subcutaneous adipose tissue was present.
- A slight elevation in body temperatures was noted in male pigs.
- Sinus tachycardia (in pigs), occurring at the 4 hour interval post dosing.
- In addition, other acceptable treatment to relieve drug-related AE's should be used at Investigator's discretion.

Study subjects must be informed of possible AEs that occurred in clinical studies (phase 0):

- At the injection site -local and transient: erythema, oedema, pruritus, anesthesia, pain, mass (subcutaneous scar).
- Abdominal abscess

26 May 2017 58 CONFIDENTIAL

• Transient moderate to severe elevation of the liver enzymes: Alanine aminotransferase (ALT) and Aspartate aminotransferase (AST).

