# Study Drug Dosage and Administration

Subjects will receive single doses of the investigational product (RZL-012) or the placebo in accordance with the following:

	Cohort 1	Cohort 2	Cohort 3	Cohort 4
Number of Subjects –	6/2	6/2	6/2	6/2
Active/Placebo				
Total Dose RZL-012	40	80	120	180
(mg)				
Dose per NOAEL*	1/6.25 th	1/3.125 th	1/2.34 th	1/1.39
Number of Injections	8	16	24	36

\* based on Human Equivalent Dose (HED) from GLP toxicology study)

The initial dose will be 40 mg RZL-012 (1/6.25th the no observed adverse effect level (NOAEL) based on Human Equivalent Dose (HED) from GLP toxicology study) with subsequent doses of 80 mg and 120 mg (1/3.125th and 1/2.34th the NOAEL based on HED). The final dose will be 180 mg RZL-012, (1/1.39the NOAEL based on HED). Subjects will receive a single treatment in multiple sites (8-48) of injection diagonally (45°) to the skin surface at 5 cm lateral to the umbilicus lateral wall. The distance between injected sites will be 2 cm (see picture below) in the first three cohorts and 1cm in the fourth cohort.

The first cohort of 6 subjects will receive 8 injections (0.1 mL each in a 2 x 4 cluster and 2 cm apart) of 40 mg RZL-012 (~1/6.25th of the NOAEL). Additional 2 subjects in the cohort will serve as control and will be injected placebo (vehicle).

[figure not shown]
If no more than 1 subject experiences intolerable side effects within 14 days following the injection of the last dosed subject, according to schedule and following the DSMB approval an additional cohort (Cohort 2) of six volunteers, as above, will receive 16 injections (0.1 mL each in a 4x4 cluster and

26 May 2017 15 CONFIDENTIAL

2 cm apart) adding up to 80 mg RZL-012 (~1/3.125th of the NOAEL). Additional 2 subjects in the cohort will serve as control and will be injected placebo (vehicle).

If no more than 1 subject experiences intolerable side effects within 14 days following the injection of the last dosed subject according to schedule and following the DSMB approval, an additional cohort (Cohort 3) of six volunteers will receive a cluster of 24 injections (0.1 mL each in a 6x4 cluster and 2 cm apart) adding up to 120 mg RZL-012 (~1/2.34th of the NOAEL). Additional 2 subjects in the cohort will serve as control and will be injected placebo (vehicle).

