#### 1.2.1.2. Safety Pharmacology

The effect of RZL-012 on the central and peripheral nervous systems was evaluated using the Functional Observational Battery (FOB) in male Sprague Dawley rats. RZL-012 was administered subcutaneously to rats (n = 8/group) as 10 mg/rat. From the results it was

concluded that RZL-012 did not affect any of the central nervous system functions tested using functional observation battery in rats.

The effect of RZL-012 was evaluated on respiratory functions in male Sprague Dawley rat using head-out plethysmography. RZL-012 was administered subcutaneously at a fixed dose of 10 recorded to cover the entire predetermined time points; Pre-dose, 1, 2, 3, and 4 h post dose. RZL-012 did not affect any of the parameters tested hence it was concluded that RZL-012 has no effects on the respiratory system at the tested dose of 10 mg/rat.

A board-certified veterinary cardiologist conducted a qualitative and quantitative review of the electrocardiograms obtained pretest, pre-dose, 4 and 24 hours post-dose following the subcutaneous injection of 500 mg 5.0 % RZL-012 or vehicle in Domestic Yorkshire Crossbred Swine. There was no effect of the subcutaneous injection of 5.0 % RZL-012 on qualitative or quantitative ECG parameters or blood pressure.

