# 1.2.2.1. Extended Single Dose Toxicity Studies

#### 1.2.2.1.1. Rats

Single subcutaneous administration of test item RZL-012 at the doses of 5, 10, and 20 mg/kg in Sprague-Dawley rats resulted in non-systemic effects and or local effects at the treated skin area. Few changes observed in haematological parameters (WBC count, neutrophils, monocytes and eosinophils) were considered secondary effects due to inflammatory response (local skin reactions). The changes observed in clinical chemistry parameters (increased BUN in males and females and increased creatinine and AST levels in females) at all the doses tested and histopathological changes in kidneys (necrosis in tubular epithelium) at 20 mg/kg were considered systemic effects. Methods and results from the extended single dose toxicity study are described in the Investigator's Brochure.

Considering skin changes as non-systemic effects and or local effects, the NOAEL was determined at 10 mg/rat with an average body weight of 246.2 g for females and 255.2 g for male, under the test conditions and doses employed.

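### Section 7.2 ties the rat BUN, creatinine and kidney findings to more than 25 times the top dose, but BUN and creatinine rose at every rat dose, and the 25 has no stated basis

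*Protocol*

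**What the plan says.** Protocol Section 7.2 opens its list by requiring that "study subjects must be informed of possible AEs that occurred in animal studies (rats and pigs"). One item names increased BUN, increased creatinine and minimal single cell necrosis of the tubular epithelium. The only dose context it gives is the "kidney in rats receiving a dose higher 25 times the highest dose in this study".

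Section 1.2.2.1.1 describes the rat toxicity study, run "at the doses of 5, 10, and 20 mg/kg in Sprague-Dawley rats". It reports "increased BUN in males and females and increased creatinine and AST levels in females) at all the doses tested", and then "histopathological changes in kidneys (necrosis in tubular epithelium) at 20 mg/kg were considered systemic effects". The same section states that the "NOAEL was determined at 10 mg/rat with an average body weight of 246.2 g for females and 255.2 g for male". Section 1.2.1.2 also doses rats per animal: "RZL-012 was administered subcutaneously to rats (n = 8/group) as 10 mg/rat".

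The synopsis gives each cohort's dose as a fraction of the NOAEL, "based on Human Equivalent Dose (HED) from GLP toxicology study". The top dose is 180 mg, stated as 1/1.39 of the NOAEL (Synopsis; Section 3.3.1).

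**The concern.** Two things do not fit together. First, Section 7.2 gives one dose context for three findings, while Section 1.2.2.1.1 separates them: the chemistry changes were present at every dose and necrosis is tied to the top dose. Someone relying on Section 7.2 alone would take the wide margin to cover all three. Second, a multiple of 25 looks far too large in a study whose top dose is printed as 1/1.39 of the NOAEL, when the necrosis dose is only twice the rat NOAEL (20 against 10).

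What is at stake is the accuracy of risk information given to investigators and intended for subjects. It is not the dose plan or any analysis.

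**Working it through.** **Inputs.** Rat doses 5, 10 and 20, NOAEL 10 mg/rat, mean weights 0.2462 kg (females) and 0.2552 kg (males), all from Section 1.2.2.1.1. Top dose 180 mg (Section 3.3.1). Minimum subject weight 75 kg (Section 5.2). Two assumptions are not in the documents: a rat-to-human divisor of 6.2 for the human equivalent dose (HED), and an upper subject weight of 120 kg. The latter is close to the BMI cap of 34.9 at 1.85 m: 34.9 × 1.85² = 119 kg.

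**Units.** Section 1.2.2.1.1 prints the doses in mg/kg and the NOAEL in mg/rat. Taken literally, 20 mg/kg in a 0.25 kg rat is about 5 mg/rat, so the highest dose would be half the stated NOAEL. The mg/rat reading is the coherent one and is used here. Then 20 mg/rat = 20/0.2552 to 20/0.2462 = 78.4 to 81.2 mg/kg, and 5 mg/rat = 19.6 to 20.3 mg/kg.

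**Step 1, no scaling needed.** The lowest dose with chemistry changes is 5/20, a quarter of the necrosis dose. If 25 is the necrosis multiple, the multiple for the lowest affected dose is 25/4 = 6.25.

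**Step 2, multiples of 180 mg.** Unscaled multiple = rat mg/kg ÷ (180/weight). HED multiple = unscaled multiple ÷ 6.2.

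| Rat dose (mg/rat) | Basis | 75 kg (2.4 mg/kg) | 120 kg (1.5 mg/kg) |
|---|---|---|---|
| 20, necrosis | unscaled | 32.7–33.8 | 52.2–54.2 |
| 20, necrosis | HED | 5.3–5.5 | 8.4–8.7 |
| 5, lowest with BUN/creatinine rise | unscaled | 8.2–8.5 | 13.1–13.5 |
| 5, lowest with BUN/creatinine rise | HED | 1.3–1.4 | 2.1–2.2 |

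**Step 3, what would be needed for 25.**
- *Lowest dose, unscaled (the most favourable basis).* Weight = 25 × 180/20.3 to 25 × 180/19.6, about 222 to 230 kg. At BMI 34.9 the lower figure needs a height of √(222/34.9) = 2.52 m.
- *Necrosis dose, HED.* Weight = 25 × 180 × 6.2/81.2 to 25 × 180 × 6.2/78.4, about 343 to 356 kg.
- *Sensitivity to the divisor.* At 120 kg, 54.2/25 = 2.2, so any divisor above about 2.2 keeps necrosis below 25 throughout 75 to 120 kg. The chemistry conclusion does not depend on the divisor.

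**Step 4, the printed NOAEL fractions.** 40 × 6.25 = 80 × 3.125 = 250 mg and 180 × 1.39 = 250.2 mg (cohort 3 is out of line: 120 × 2.34 = 281 mg). *If* 250 mg is the HED of the rat NOAEL, which the documents do not state, necrosis corresponds to 250 × 20/10 = 500 mg, and 500/180 = 2.8.

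**Step 5, where 25 could come from.** On the Step 4 assumption, 500 mg over the phase 0 top dose of 20 mg (Section 1.2.4, Table 1) is exactly 25. The synopsis text for cohort 4 also still prints 240 mg. At 75 kg that is 3.2 mg/kg, and 78.4/3.2 to 81.2/3.2 = 24.5 to 25.4 unscaled. Both routes fit.

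**The case against.** Section 7.2 does not say that the findings appeared only above 25 times the top dose. All three did occur at the 20 dose, so the sentence is incomplete rather than strictly contradicted. It is also loosely built, and the dose phrase may belong to the necrosis alone. Nor does it mention HED: on a plain mg/kg comparison, 20 mg/rat exceeds 25 times 180 mg for every subject of 75 kg or more. All of this stands. It means the necrosis multiple lacks a stated basis; it is not a proven arithmetic error.

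It does not rescue the chemistry findings. Even unscaled, the lowest affected dose is far short of 25 in any eligible subject. If the phrase covers necrosis alone, Section 7.2 gives no dose context for BUN and creatinine.

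Three stronger readings are tempting, and the documents do not support them:
- *That the chemistry changes began below the top human dose* (125/180 = 0.7). This needs 250 mg to be the rat NOAEL. Section 3.2 names no species, and direct conversion of 10 mg/rat (39.2 to 40.6 mg/kg, divisor 6.2, 75 kg) gives about 474 to 491 mg, not 250. Reading the doses literally as mg/kg also gives multiples near or below 1, but that reading conflicts with the stated NOAEL.
- *That the 25 was carried over from phase 0.* The fit is exact, but it uses the same assumption and is not the only fit.
- *That subjects were misinformed.* The consent text is not available to this review. The protocol copy is numbered 001.2 and dated 26 May 2017, while the SAP cites V1.4 of 4 March 2018, so later wording may differ.

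**Conclusion.** The point holds for the chemistry findings without any scaling assumption: Section 7.2 gives 25 as their only dose context, while Section 1.2.2.1.1 puts them at every dose tested. On the mg/rat reading, the lowest affected dose is about 8 times the top dose unscaled at 75 kg, and about 1.3 to 2.2 times by HED.

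For necrosis, the figure is unsupported rather than shown to be false. It is met on an unscaled basis. It is not met on the HED basis the protocol uses for its margins, where the multiple is about 5 to 9 (assumed divisor 6.2, 75 to 120 kg), or 2.8 if the 250 mg reference is the rat NOAEL.

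The consequence is minor. No dose, stopping rule or analysis uses the 25. The NOAEL fractions are printed openly, Section 1.2.2.1.1 gives investigators the all-doses finding, and serum chemistry including creatinine and BUN is drawn on Days 1, 3, 7, 14 and 28 (Section 6.1.8.2). It still merits correction, because Section 7.2 sets out what subjects must be told.

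**What to change.** - In Section 7.2, say that BUN rises (both sexes) and creatinine rises (females) were seen at all rat doses tested, and tubular necrosis at the highest.
- After checking the toxicology report, replace the 25 with the multiple for 180 mg on the HED basis, and state that basis: species, dose units, conversion and body weight.
- In Section 1.2.2.1.1, correct the mg/kg versus mg/rat label.
- Carry the correction into the consent text if the figure appears there.

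The cost is one check of the toxicology report and a wording change. The stated renal margin becomes less favourable. No visits, samples or design features change.

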### 7.3. PREMATURE DISCONTINUATION FROM STUDY

Study will be prematurely discontinued in any of the following cases:

- Subject's request.
- Any life-threatening (i.e., Grade 4) adverse event may cause prematurely discontinuation.
- Systemic hypersensitivity reaction may cause prematurely discontinuation.
- Any Grade 3 or 4 ADR (defined in Section 9.3) clinically evaluated by the PI and/or Sponsor as warranting subject discontinuation.
- Non-compliance: Subject's non-compliance with study procedures as evaluated by PI and/or Sponsor as warranting subject discontinuation.
- Other reasons regarded by PI as warranting subject's discontinuation.
- Premature study termination as described in Section 7.4.

Subjects who discontinue the study prematurely will be queried whether an adverse event contributed to their decision.

